**Table 1: Single Dose\* Escalation**

Cohort 1 - fasting	6 subjects**	Single 40 mg VT-1598 tablet	Safety data for Cohort 1 subjects through Day 7 will be confirmed by reviewing objective pre-defined criteria before continuing to Cohort 2.
	Dose: 40 mg	2 subjects**	
Cohort 2 - fasting	6 subjects**	Two 40 mg VT-1598 tablets	Safety data for Cohort 2 subjects through Day 7 will be confirmed by reviewing objective pre-defined criteria before continuing to Cohort 3.
	Dose: 80 mg	2 subjects**	
Cohort 3 - fasting	6 subjects**	Four 40 mg VT-1598 tablets	Safety data for Cohort 3 subjects through Day 7 will be confirmed by reviewing objective pre-defined criteria before continuing to Cohort 4 and 6. Interim analysis of PK data (Cohorts 1-3)***
	Dose: 160 mg	2 subjects**	
Cohort 4 – fasting	6 subjects**	Four 80 mg VT-1598 tablets	Cumulative safety data for all subjects in Cohorts 1-4 through Day 21 will be reviewed by the SMC for recommendation/confirmation of dosing before continuing to Cohort 5
	Dose: 320 mg	2 subjects**	
Cohort 5 – fasting	6 subjects**	Eight 80 mg VT-1598 tablets	
	Dose: 640 mg	2 subjects**	
Cohort 6 – fed (high-fat, high- calorie meal)	6 subjects	Four 40 mg VT-1598 tablets	Cohort 6 is comprised of the same subjects as Cohort 3****. These subjects will receive the same treatment in Cohort 6 as Cohort 3. Cohort 6 may start enrolling prior to convening the SMC meeting and prior to the start of Cohort 5.
	Dose: 160 mg	2 subjects	

[figure not shown]
\*Dose refers to the free base equivalent of the drug.

\*\*Within each fasted cohort two sentinel subjects will be admitted initially, and the randomization scheme will be designed to ensure that one subject will receive VT-1598 and the other will receive placebo. All sentinel subject safety data through Day 3 is reviewed by PI prior to dosing remainder of cohort.

\*\*\*PK data only; enrollment for Cohort 4 will not stop for the PK interim analysis.

\*\*\*\* The Cohort 6 replacement subjects will receive the same treatment as assigned to the Cohort 3 subject they are replacing.

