2.1. Purpose of the Analyses

This SAP describes safety and PK analyses of 40 mg, 80 mg, 160 mg, 320 mg, and 640 mg of VT-1598 given orally under a fasted state; and of 160 mg of VT-1598 given orally under a fed state (after administration of a high-fat, high calorie meal). PK analyses include assessment of VT-1598 and its primary metabolite, VT-11134.

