The **t_{1/2}** is defined as the time required for the drug or metabolite concentration to decrease by a factor of one-half in the terminal phase. The **t_{1/2}** can be estimated as $\ln(2)/\lambda z$. It will be obtained from the **HL_Lambda_z** parameter calculated by WinNonlin. Half-life will be reported in units of h.

AUC

$AUC_{0-\text{last}}$ is defined as the area under the concentration-time curve from dosing (time 0) to the time of the last measured concentration. $AUC_{0-\text{last}}$ will be estimated using the Linear Up Log Down calculation method and obtained from the **AUClast** parameter calculated by WinNonlin.

$AUC_{0-\text{inf}}$ is defined as the total area under the concentration-time curve from dosing (time 0) taken to the limit as the end time becomes arbitrarily large. $AUC_{0-\text{inf}}$ can be calculated by adding $AUC_{0-\text{last}}$ to an extrapolated value equal to the last measured concentration greater than the LLOQ divided by λz :

$$AUC_{0-\text{inf}} = AUC_{0-\text{last}} + \frac{C_{\text{last}}}{\lambda z}$$

Where C_{last} is the last measured concentration \geq LLOQ. $AUC_{0-\text{inf}}$ will be obtained from the **AUCINF_obs** parameter calculated by WinNonlin®.

% AUC_{ex} is defined as percentage of $AUC_{0-\text{inf}}$ obtained by extrapolation from time of the last measured concentration to infinity. % AUC_{ex} can be calculated by dividing AUC from time of the last measured concentration to infinity by $AUC_{0-\text{inf}}$:

$$\%AUC_{\text{ex}} = \frac{AUC_{0-\text{inf}} - AUC_{0-\text{last}}}{AUC_{0-\text{inf}}},$$

If % AUC_{ex} is $>20\%$, the estimated $AUC_{0-\text{inf}}$ will be excluded from statistical summaries of PK parameter estimates and downstream calculations. % AUC_{ex} will be obtained from the **AUC_%Extrap_obs** parameter calculated by WinNonlin.

All AUCs will be reported in units of ng*h/mL.

CL/F

Apparent oral clearance (CL/F) will be obtained from Dose/ AUC_{inf} . If % AUC_{ex} is $>20\%$, the estimated CL/F value will be excluded from statistical summaries of parameter estimates and downstream calculations. CL/F will be obtained from the **CL_F_obs** parameter calculated by WinNonlin. Clearance will be reported in units of L/h.

V_d/F

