Apparent volume of distribution (V_d/F) will be calculated as $(CL/F)/\lambda z$. If % AUC_{ex} is $>20\%$, the estimated V_d/F value will be excluded from statistical summaries of parameter estimates and downstream calculations. V_d/F will be obtained from **Vz_F_obs** calculated by WinNonlin. Volume will be reported in units of L.

Ae_{last}

Ae_{last} is defined as the cumulative amount of drug or metabolite excreted into urine up to the collection time of the last measurable concentration. Amount of drug or metabolite will be reported in units of mg.

$Ae\%_{\text{Dose}}$

$Ae\%_{\text{Dose}}$ is defined as the percent of drug (VT-1598) excreted into urine up to the ending time of the last measurable concentration. $Ae\%_{\text{Dose}}$ will be obtained from $Ae_{\text{last}}/\text{Dose} * 100\%$.

CL_R

CL_R is defined as the renal clearance of drug or metabolite and will be calculated as Ae_{last}/AUC_{0-t1}. Where AUC_{0-t1} is defined as AUC from dosing (time 0) to collection time (t1) based on the last collected concentration in urine (0 h to 72 h post dose). AUC_{0-t1} will be converted to mg*min/mL for calculations of CL_R. CL_R will be treated a missing if AUC_{0-t1} or Ae_{last} is not estimable. Renal clearance of VT-1598 or VT-11134 will be reported in units of mL/min.

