PK Parameter (Units)	40 mg Fasted	80 mg Fasted	160 mg Fasted	160 mg Fed	320 mg Fasted	640 mg Fasted
C _{max} , (ng/mL)	x (x)	x (x)	x (x)	x (x)	x (x)	x (x)
C _{max} /Dose, ((ng/mL)/mg)	x (x)	x (x)	x (x)	x (x)	x (x)	x (x)
T _{max} , (h)	x (x - x)	x (x - x)	x (x - x)	x (x - x)	x (x - x)	x (x - x)
AUC _(0-last) , (ng*h/mL)	x (x)	x (x)	x (x)	x (x)	x (x)	x (x)
AUC _(0-last) , Dose ((ng*h/mL)/mg)	x (x)	x (x)	x (x)	x (x)	x (x)	x (x)
AUC _(0-inf) , (ng*h/mL)	x (x)	x (x)	x (x)	x (x)	x (x)	x (x)
AUC _(0-inf) /Dose, ((ng*h/mL)/mg)	x (x)	x (x)	x (x)	x (x)	x (x)	x (x)
λ _Z , (1/h)	x (x)	x (x)	x (x)	x (x)	x (x)	x (x)
t _{1/2} , (h)	x (x)	x (x)	x (x)	x (x)	x (x)	x (x)
CL/F, (L/h)	x (x)	x (x)	x (x)	x (x)	x (x)	x (x)
V _d /F, (L)	x (x)	x (x)	x (x)	x (x)	x (x)	x (x)

Note: Values of GM (CV %) are shown, except for T_{max} for which values of median (min-max) are shown.

Table 74: Summary Statistics for VT-1598 PK Parameters in Plasma, 40 mg Fasted Dose Group

Statistics	C _{max} (ng/mL)	C _{max} /Dose ((ng/mL)/mg)	T _{max} (h)	AUC _{0-last} (ng*h/mL)	AUC _{0-last} /Dose ((ng*h/mL)/mg)	AUC _{0-inf} (ng*h/mL)	AUC _{0-inf} /Dose ((ng*h/mL)/mg)	Δz (1/h)	CL/F (L/h)	V _d /F (L)
N	x	x	x	x	x	x	x	x	x	x
Mean	x	x	x	x	x	x	x	x	x	x
SD	x	x	x	x	x	x	x	x	x	x
Min	x	x	x	x	x	x	x	x	x	x
Max	x	x	x	x	x	x	x	x	x	x
CV %	x	x	x	x	x	x	x	x	x	x
GM	x	x	x	x	x	x	x	x	x	x

Table 75: Summary Statistics for VT-1598 PK Parameters in Plasma, 80 mg Fasted Dose Group

This table will repeat Table 74 for VT-1598 PK parameters in Plasma for the 80 mg Fasted Dose Group

Table 76: Summary Statistics for VT-1598 PK Parameters in Plasma, 160 mg Fasted Dose Group

This table will repeat Table 74 for VT-1598 PK parameters in Plasma for the 160 mg Fasted Dose Group

Table 77: Summary Statistics for VT-1598 PK Parameters in Plasma, 160 mg Fed Dose Group

This table will repeat Table 74 for VT-1598 PK parameters in Plasma for the 160 mg Fed Dose Group

Table 78: Summary Statistics for VT-1598 PK Parameters in Plasma, 320 mg Fasted Dose Group

This table will repeat Table 74 for VT-1598 PK parameters in Plasma for the 320 mg Fasted Dose Group

Table 79: Summary Statistics for VT-1598 PK Parameters in Plasma, 640 mg Fasted Dose Group

This table will repeat Table 74 for VT-1598 PK parameters in Plasma for the 640 mg Fasted Dose Group

Table 80: Summary Statistics for VT-11134 PK Parameters in Plasma by Dose Group

This table will repeat Table 73 for VT-11134 PK parameters in plasma, by Dose Group

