Table 81: Summary Statistics for VT-11134 PK Parameters in Plasma, 40 mg Fasted Dose Group

This table will repeat Table 74 for VT-11134 PK parameters in plasma for the 40 mg Fasted Dose Group

Table 82: Summary Statistics for VT-11134 PK Parameters in Plasma, 80 mg Fasted Dose Group

This table will repeat Table 74 for VT-11134 PK parameters in Plasma for the 80 mg Fasted Dose Group

Table 83: Summary Statistics for VT-11134 PK Parameters in Plasma, 160 mg Fasted Dose Group

This table will repeat Table 74 for VT-11134 PK parameters in Plasma for the 160 mg Fasted Dose Group

Table 84: Summary Statistics for VT-11134 PK Parameters in Plasma, 160 mg Fed Dose Group

This table will repeat Table 74 for VT-11134 PK parameters in Plasma for the 160 mg Fed Dose Group

Table 85: Summary Statistics for VT-11134 PK Parameters in Plasma, 320 mg Fasted Dose Group

This table will repeat Table 74 for VT-11134 PK parameters in Plasma for the 320 mg Fasted Dose Group

Table 86: Summary Statistics for VT-11134 PK Parameters in Plasma, 640 mg Fasted Dose Group

This table will repeat Table 74 for VT-11134 PK parameters in Plasma for the 640 mg Fasted Dose Group

Table 87: Summary Statistics for VT-1598 PK Parameters in Urine by Dose Group

	40 mg Fasted	80 mg Fasted	160 mg Fasted	160 mg Fed	320 mg Fasted	640 mg Fasted
Inpatient Period (0-72 h)^a						
Ae _{last} (mg)	x (xx, xx)	x (xx, xx)	x (xx, xx)	x (xx, xx)	x (xx, xx)	x (xx, xx)
Ae%Dose (%)	x (xx, xx)	x (xx, xx)	x (xx, xx)	x (xx, xx)	x (xx, xx)	x (xx, xx)
CL _R (mL/min)	x (x)	x (x)	x (x)	x (x)	x (x)	x (x)
Nominal Collection Time Interval^a						
Ae ₀₋₆ (mg)	x (xx, xx)	x (xx, xx)	x (xx, xx)	x (xx, xx)	x (xx, xx)	x (xx, xx)
Ae ₆₋₁₂ (mg)	x (xx, xx)	x (xx, xx)	x (xx, xx)	x (xx, xx)	x (xx, xx)	x (xx, xx)
Ae ₁₂₋₂₄ (mg)	x (xx, xx)	x (xx, xx)	x (xx, xx)	x (xx, xx)	x (xx, xx)	x (xx, xx)
Ae ₂₄₋₃₆ (mg)	x (xx, xx)	x (xx, xx)	x (xx, xx)	x (xx, xx)	x (xx, xx)	x (xx, xx)
Ae ₃₆₋₄₈ (mg)	x (xx, xx)	x (xx, xx)	x (xx, xx)	x (xx, xx)	x (xx, xx)	x (xx, xx)
Ae ₄₈₋₆₀ (mg)	x (xx, xx)	x (xx, xx)	x (xx, xx)	x (xx, xx)	x (xx, xx)	x (xx, xx)
Ae ₆₀₋₇₂ (mg)	x (xx, xx)	x (xx, xx)	x (xx, xx)	x (xx, xx)	x (xx, xx)	x (xx, xx)

Note: Values of Mean (Min, Max) are shown, except for CL_R, for which values of GM (CV %) are shown.

^a Times are relative to time of dosing.

Table 88: Summary Statistics for VT-1598 PK Parameters in Urine, 40 mg Fasted Dose Group

Statistics	Inpatient Period (0-72 h) ^a			Nominal Collection Time Interval ^a						

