Dose Group	Analyte	Subject ID	Nominal Collection Interval ^a	Actual Collection Interval ^a	Laboratory Reported Concentration (ng/mL)	Urine Volume (mL)	Analysis Concentrations (ng/mL)	Total Amount Excreted From Urine (mg)
40 mg Fasted	VT-1598	PHU.00123	0-6 h	0-6 h	0	100	0	No

^aTimes are relative to time of dose. For actual time, out of window times are indicated by an asterisk (*) and imputed times are indicated by three asterisks (***).

BQL=Below Quantitative Limit

Listing 32: Subject Specific VT-1598 Plasma PK Parameters

[Implementation Note: Sort order: Dose Group, Subject ID.]

Dose Group	Subject ID	C _{max} (ng/mL)	C _{max} /Dose (ng/mL/mg)	T _{max} (h)	AUC _{0-last} (ng*h/mL)	AUC _{0-last} /Dose ((ng*h/mL)/mg)	AUC _(0-inf) (ng*h/mL)	AUC _(0-inf) /Dose ((ng*h/mL)/mg)	λz (1/h)	t _{1/2} (h)	CL/F (L/h)	V _d /F (L)

Listing 33: Subject Specific VT-11134 Plasma PK Parameters

This listing will repeat Listing 32 for VT-11134 PK parameters in plasma.

Listing 34: Subject Specific VT-1598 Urine Inpatient Period PK Parameters

[Sort Order: Dose Group (40 mg Fasted, 80 mg Fasted, 160 mg Fasted, 160 mg Fed, 320 mg Fasted, 640 mg Fasted), Subject ID.]

Dose Group	Subject ID	A _e last (mg)	A _e %Dose (%)	CLR (mL/min)
x	x	x	x	x
x	x	x	x	x
x	x	x	x	x
x	x	x	x	x
x	x	x	x	x
x	x	x	x	x
x	x	x	x	x

Listing 35: Subject Specific VT-1598 Urine Nominal Collection Time Interval PK Parameters

[Sort Order: Dose Group (40 mg Fasted, 80 mg Fasted, 160 mg Fasted, 160 mg Fed, 320 mg Fasted, 640 mg Fasted), Subject ID.]

Dose Group	Subject ID	Ae ₀₋₆ (mg)	Ae ₆₋₁₂ (mg)	Ae ₁₂₋₂₄ (mg)	Ae ₂₄₋₃₆ (mg)	Ae ₃₆₋₄₈ (mg)	Ae ₄₈₋₆₀ (mg)	Ae ₆₀₋₇₂ (mg)
x	x	x	x	x	x	x	x	x
x	x	x	x	x	x	x	x	x
x	x	x	x	x	x	x	x	x
x	x	x	x	x	x	x	x	x
x	x	x	x	x	x	x	x	x
x	x	x	x	x	x	x	x	x
x	x	x	x	x	x	x	x	x

Listing 36: Subject Specific VT-11134 Urine Inpatient Period PK Parameters

[Sort Order: Dose Group (40 mg Fasted, 80 mg Fasted, 160 mg Fasted, 160 mg Fed, 320 mg Fasted, 640 mg Fasted), Subject ID.]

Dose Group	Subject ID	Ae _{last} (mg)	CLR (mL/min)
x	x	x	x
x	x	x	x
x	x	x	x
x	x	x	x
x	x	x	x
x	x	x	x
x	x	x	x

Listing 37: Subject Specific VT-11134 Urine Nominal Collection Time Interval PK Parameters

This table will repeat Listing 35 for VT-11134 in urine.

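### CL/F and Vd/F for the metabolite VT-11134 would be calculated from the VT-1598 dose, so the reported values would not be the metabolite's apparent clearance or volume

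*SAP*

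**What the plan says.** SAP 2.1 sets the scope: "PK analyses include assessment of VT-1598 and its primary metabolite, VT-11134". SAP 10.2 then plans plasma parameter summaries for both analytes, with Table 73 for VT-1598 and Table 80 for VT-11134.

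- **Shells.** Table 73 has CL/F (L/h) and Vd/F (L) rows. The instruction for Table 80 is "This table will repeat Table 73 for VT-11134 PK parameters in plasma, by Dose Group". Table 74 has the same two parameters as columns, and the first metabolite table built on it reads "This table will repeat Table 74 for VT-11134 PK parameters in plasma for the 40 mg Fasted Dose Group"; Tables 82-86 follow the same pattern. Listing 32 also carries both columns, and for the metabolite "This listing will repeat Listing 32 for VT-11134 PK parameters in plasma". None of these places has an exclusion, a footnote, a fraction-metabolised term or a molar conversion.
- **Definitions, SAP 10.2.** There is one entry for each parameter. "Apparent oral clearance (CL/F) will be obtained from Dose" divided by AUCinf is the first. "Apparent volume of distribution (V_d/F) will be calculated as" (CL/F)/lambda_z is the second. Neither is restricted to VT-1598, and the lambda_z entry, which covers drug or metabolite, lists both among the parameters derived from it.
- **What Dose means.** The note to Protocol Table 1 says "Dose refers to the free base equivalent of the drug". No cohort receives VT-11134.
- **Urine, by contrast.** Ae%Dose "is defined as the percent of drug (VT-1598) excreted into urine", and the VT-11134 urine outputs (Tables 94-95, Listing 36) leave it out.
- **Protocol 10.6** applies its parameter list to both analytes as appropriate and defers detail to the SAP.

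**The concern.** Dose/AUCinf estimates CL/F for a compound when the numerator is the dose of that compound. Here the numerator is the parent dose and the denominator is the metabolite AUC. The result mixes the metabolite's clearance with how much parent is absorbed, how much of that becomes VT-11134, and the mass difference between the two molecules. Printed as CL/F in L/h and Vd/F in L, beside parent values bearing the same labels, the numbers invite a direct comparison that is not valid.

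The SAP applied the right logic to the one dose-based urine parameter by limiting it to the parent. The plasma shells did not get the same treatment, which suggests that the repeat-the-table shorthand was not tailored rather than that a method was chosen. What is at stake is the correctness of two reported parameters for an analyte whose PK profile is a stated secondary objective.

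**Working it through.** The plan states no figure to reproduce. The check is a trace of the definitions followed by algebra.

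**Trace.** Table 80 copies Table 73, Tables 81-86 copy Table 74, and Listing 33 copies Listing 32. Each source contains CL/F = Dose/AUCinf and Vd/F = (CL/F)/lambda_z. The only dose in the trial is VT-1598, so for VT-11134 the formula becomes parent dose divided by metabolite AUCinf.

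**CL/F.** Let F be the fraction of the dose absorbed, fm the fraction of absorbed VT-1598 converted to VT-11134, R the metabolite/parent molecular-weight ratio, and CLm the metabolite's clearance. The mass of metabolite formed is F x fm x R x Dose, so

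- AUCm = F x fm x R x Dose / CLm
- Dose/AUCm = CLm / (F x fm x R)

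Relative to CLm/F, the reported value is too large by 1/(fm x R). It is correct only if fm x R = 1. Protocol 4.1 gives the molecular weight of VT-1598 (584.5 g/mol), but the documents give neither the molecular weight of VT-11134 nor fm. The values below are therefore assumptions that show a range.

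| assumed fm | factor, R = 1 | factor, R = 0.6 |
|---|---|---|
| 1 | 1 | 1.67 |
| 0.5 | 2 | 3.33 |
| 0.25 | 4 | 6.67 |
| 0.1 | 10 | 16.7 |
| 0.05 | 20 | 33.3 |

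**Vd/F.** Two cases need separating.

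- If lambda_z is the metabolite's own rate constant (CLm/Vm), the factor relative to Vm/F is again 1/(fm x R).
- If the metabolite is formation-limited, its terminal slope is the parent's. The factor becomes [1/(fm x R)] x [(CLm/Vm)/lambda_z].

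A one-compartment parent and one-compartment metabolite model illustrates the second case. The assumed inputs are F = 1, dose 160 mg, absorption rate 0.5/h, parent CL 2 L/h and V 200 L, metabolite CLm 5 L/h and Vm 100 L. The parent rate is 2/200 = 0.010/h and the metabolite's own rate is 5/100 = 0.050/h. The fitted metabolite lambda_z was 0.0100/h, which is the parent's.

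- fm = 1, R = 1: Dose/AUCm = 5.00 L/h, which is correct. Vd/F = 5.00/0.0100 = 500 L against a true 100 L, a factor of 5.
- fm = 0.1, R = 1: Dose/AUCm = 50.00 L/h, a factor of 10. Vd/F = 50.00/0.0100 = 5,000 L, a factor of 50.

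So Vd/F can be wrong even when fm = 1.

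**What removal would lose.** Table 73 already has an AUCinf/Dose row in (ng*h/mL)/mg. Since 1 mg/(ng*h/mL) = 10^6 mL/h = 1,000 L/h, CL/F in L/h equals 1,000 divided by that row for each subject. Dropping CL/F for VT-11134 discards no information.

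**The case against.** The strongest reply is that CL/F is already an apparent quantity, scaled by an unknown F. On that view, for a metabolite the same ratio is understood as CLm/(F x fm), a legitimate quantity with an incomplete label. Part of this stands: the ratio is well defined, and relabelling is an acceptable remedy. But the SAP nowhere says that the metabolite version includes fm, makes no molar correction, and uses one label for two different quantities. The argument also does not rescue Vd/F when lambda_z belongs to the parent.

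A second reply is that Protocol 10.6 allows parameters to be omitted where not appropriate, and that SAP 10.2 uses drug-or-metabolite wording for Cmax, lambda_z and half-life but not for CL/F or Vd/F. It is also true that the SAP never states in words that the parent dose will be divided by the metabolite AUC. That leaves room to omit the parameters. The shells, however, include them, and the lambda_z entry names them as derived parameters, so a programmer following the SAP would produce them.

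Third, some cells may be empty. Both parameters are missing when the lambda_z criteria fail, and they leave the summaries when extrapolation exceeds 20%. That reduces how many wrong values appear but does not make the rest right.

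A reader might infer more than the documents support:

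- *That the values would mislead later dose selection.* Nothing in either document uses VT-11134 CL/F or Vd/F for that.
- *That the metabolite PK assessment as a whole is unsound.* It is not: VT-11134 Cmax, AUC, Tmax and half-life do not use these parameters, and CL_R divides the analyte's own urinary amount by its own AUC. Dose proportionality (SAP 10.3.1) and the food-effect comparisons (SAP 10.3.2 and 10.3.3) rest on Cmax, AUC and Tmax.
- *That 1/fm measures the error in both parameters.* It applies to CL/F relative to CLm/F with R = 1, and does not by itself determine the error in Vd/F.

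**Conclusion.** Wrong as written, with limited reach. If the SAP is followed, Tables 80-86 and Listing 33 will show VT-11134 values under CL/F and Vd/F labels that do not match what was calculated. CL/F would be inflated by 1/(fm x R) relative to CLm/F; with R = 1 and assumed fm between 0.5 and 0.1, that is 2-fold to 10-fold. The actual size cannot be computed from the documents. The direction of the CL/F error follows from fm and R each being at most 1 and at least one below 1; for R this assumes that VT-11134 is no heavier than its parent. The Vd/F error has no single factor, because it also depends on whether VT-11134 is formation-limited. The consequence is confined to descriptive secondary PK output, and no safety or inferential result changes.

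**What to change.** **Preferred.** Remove CL/F and Vd/F from Tables 80-86 and Listing 33, and state in SAP 10.2 that both parameters are calculated for VT-1598 only, in line with Ae%Dose. Keep Cmax, Tmax, the AUCs and lambda_z, and keep half-life where the shell has it (Table 73 and Listing 32 do, Table 74 does not). The dose-normalised rows can stay if a footnote says that they are per mg of VT-1598.

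**Alternative.** Relabel the parameters CLm/(F x fm) and Vm/(F x fm), use a molar-corrected dose (Dose x R), and add a footnote that they are not the metabolite's clearance or volume. This needs the VT-11134 molecular weight. The volume label also needs the caveat that it fails if lambda_z reflects the parent.

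**Optional.** Add metabolite-to-parent ratios for AUC and Cmax, which describe relative exposure without needing fm or F.

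**Cost.** A shell edit and one sentence in SAP 10.2; no new data and no loss of information. SAP Section 15 already reports one analysis in the past tense, so outputs may exist. In that case the change can be made in the clinical study report, where SAP Section 1 requires deviations to be described and justified.

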5. SAMPLE SIZE CONSIDERATIONS

This is a Phase 1 FIH study to assess the safety and PK of VT-1598. Since the study is primarily aimed at safety and PK evaluation, no formal power calculations based on testing a statistical hypothesis were constructed. The sample size of 8 subjects (6 subjects receiving VT-1598 and 2 subjects receiving placebo) per cohort is based on clinical experience and judgement and should provide adequate clinical information to meet the study objectives. The comparisons of PK between the fasted and fed cohorts (Cohort 3 and Cohort 6) are exploratory rather than formal analyses of fed bioequivalence. Fasted and fed PK profiles from 6 subjects are sufficient to meet the intended purpose.

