10.3.2. Analysis of Change in T_{max} between Fasted and Fed Dose Groups

The difference in median T_{max} values and the corresponding 90% CI for the difference between the 160 mg Fasted Dose Group and Fed Dose Group will be estimated using the PK Analysis Subset. An exact Wilcoxon signed-rank test will be conducted to compare T_{max} between subjects who participated in both cohorts. This paired analysis will only be conducted if there are at least 3 individual subjects in the PK Analysis Population who are in Cohort 3 as well as Cohort 6. An exact Wilcoxon rank sum test will be used to compare the difference in median T_{max} between all subjects in the 160 mg Fasted Dose Group to the 160 mg Fed Dose Group, regardless of whether the subject participated in both dosing periods. Continuity corrections will not be used for either test. Results from the paired and unpaired comparison of changes in T_{max} will be presented in [Table 102](#).

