15. SUMMARY OF CHANGES IN THE CONDUCT OF THE STUDY OR PLANNED ANALYSES

Only one subject from the fasted 160 mg cohort (Cohort 3) returned for the fed 160 mg cohort (Cohort 6). This impacts the planned analysis of change in T_{max} between fasted and fed Dose Groups. Previously, an exact Wilcoxon-signed rank test had been proposed to compare subjects who had participated in both cohorts, however since fewer than 3 subjects were present in both cohorts, this analysis was not completed. Instead, only an exact Wilcoxon rank sum test was performed to compare the change in T_{max} between fasted and fed Dose Groups.

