Note: β -hat is an estimate obtained using the linear model $\log(\text{Param}) = \alpha + \text{dose} \times \beta$, where Param is AUC_{0-last}, AUC_{0-inf}, or C_{max}. Perfect dose proportionality is equivalent to $\beta = 1$. The value ρ is equivalent to the ratio of the highest dose included in the analysis divided by the lowest dose included in the analysis. Presence of dose proportionality is concluded when the 90% confidence interval for $\rho^{\beta\text{-hat}-1}$ is contained within the interval (0.80,1.25).

Table 102: Comparison of T_{max} between Fasted and Fed 160 mg Dose Groups

[Implementation Note: Since fewer than 3 subjects in the PK Analysis Population were in both Cohort 3 and Cohort 6 then the Wilcoxon signed-rank test comparing T_{max} (Paired) between the cohorts will not be conducted. The N, Estimate, and 90% CI cells should be “-“ and a footnote should be added to explain why they are missing.]

Parameter	Estimand	Subjects Included	VT-1598			VT-11134		
			N ^a	Estimate	90% CI ^b	N ^a	Estimate	90% CI ^b
T _{max} (Paired)	Median of (160 mg Fed T _{max}) - (160 mg Fasted T _{max})	Subjects who received 160 mg of VT-1598 in both Cohort 3 (Fast) and Cohort 6 (Fed).	x	x	(x, x)	x	x	(x, x)
T _{max} (Independent)	(160 mg Fed T _{max} Median) - (160 mg Fasted T _{max} Median)	Any subject who received 160 mg of VT-1598 in either Cohort 3 (Fast) or Cohort 6 (Fed)	x	x	(x, x)	x	x	(x, x)

^a N=Number of subjects with data used to compute T_{max}. In the paired comparison, data was used from any subject in the PK Analysis Subset who received 160 mg VT-1598 under both a fasted and fed state. In the independent comparison, data was used from any subject in the PK Analysis Subset who received 160 mg VT-1598 under either a fasted or fed state, regardless of whether or not the subject participated in both study parts.

^b The 90% CI for subjects who receive VT-1598 and participated in both cohorts was calculated using Wilcoxon signed-rank test. The 90% CI for all subjects who received VT-1598 in either cohort was calculated using a Wilcoxon rank sum test.

Table 103: Comparison of Plasma PK Exposure Parameters between Fasted and Fed 160 mg Dose Groups – VT-1598

Exposure Parameter Comparison	VT-1598			VT-11134		
	N ^a	Estimate	90% CI ^b	N ^a	Estimate	90% CI ^b
C _{max} Ratio (Fed/Fast)	x	x	(x, x)	x	x	(x, x)
AUC _(0-last) Ratio (Fed/Fast)	x	x	(x, x)	x	x	(x, x)
AUC _(0-inf) Ratio (Fed/Fast)	x	x	(x, x)	x	x	(x, x)

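### In the unpaired Tmax food-effect row, the estimate is labelled as a difference in medians but the 90% CI comes from the rank-sum test, whose matching estimate is the Hodges-Lehmann shift

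*SAP*

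**What the plan says.** SAP 10.3.2 asks for the difference in median Tmax "and the corresponding 90% CI for the difference between the 160 mg Fasted Dose Group and Fed Dose Group". For the unpaired comparison it continues: "An exact Wilcoxon rank sum test will be used to compare the difference in median" Tmax between all subjects in the two 160 mg groups. It adds that "Continuity corrections will not be used for either test".

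SAP Appendix 1, Table 102 turns this into a row for each analyte with an estimand, an estimate and a 90% CI. In the independent row the estimand is the fed Tmax median minus the fasted Tmax median (the printed expression contains "Median) - (160 mg Fasted"). Footnote b states how the interval is obtained: "The 90% CI for all subjects who received VT-1598 in either cohort was calculated using a Wilcoxon rank sum test".

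Neither place names a Hodges-Lehmann estimate, states a location-shift assumption, or specifies an interval method for a difference in medians.

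SAP 15 records that a single Cohort 3 subject returned for Cohort 6, so the paired signed-rank analysis was dropped and "only an exact Wilcoxon rank sum test was performed to compare the change in" Tmax. The independent row is therefore the only formal Tmax food-effect comparison that will contain numbers.

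**The concern.** A point estimate and the interval beside it should describe the same quantity. Inverting the rank-sum test means keeping every shift that the test does not reject. The limits of that interval are order statistics of all pairwise fed-minus-fasted differences, and the corresponding point estimate is the median of those differences. Subtracting one sample median from the other is a different statistic.

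The effect of a meal on the PK profile is a stated secondary objective. As the row is specified, two programmers could fill the estimate cell differently. One would follow the estimand column and subtract medians. The other would follow the footnote and take the shift estimate that goes with the rank-sum interval. A reader of the study report could not tell which had been done.

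**Working it through.** The documents give no Tmax result, so there is no stated figure to reproduce. The check derives the interval the plan calls for and compares the two candidate estimates.

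**Inputs from the documents.** Six subjects on active drug per group (SAP 5: "Fasted and fed PK profiles from 6 subjects are sufficient to meet the intended purpose"); exact rank-sum test, 90% confidence, no continuity correction (SAP 10.3.2, Table 102); nominal sampling times (protocol Table 2).

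**Inputs assumed.** The Tmax distributions are assumed, because the documents give none.

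**Step 1: the interval at 6 v 6.** There are C(12,6) = 924 equally likely rank arrangements and 6 × 6 = 36 pairwise differences. The largest tail not exceeding 5% holds 43 arrangements: 43/924 = 4.65%. The interval therefore runs from the 8th to the 29th ordered difference, with coverage 1 − 2 × 43/924 = 90.7%. That figure presumes no ties and independent groups. The matching point estimate is the mean of the 18th and 19th ordered differences.

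**Step 2: a worked example (assumed data).** Fasted: 3, 3, 3, 4, 6, 6 h. Fed: 4, 4, 4, 10, 12, 24 h.

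- Difference in medians: (4 + 10)/2 − (3 + 4)/2 = 7 − 3.5 = 3.5 h.
- Ordered pairwise differences: −2 (six times), 0 (three), 1 (nine), 4, 4, 6, 6, 6, 7, 7, 7, 8, 9, 9, 9, 18, 18, 20, 21, 21, 21.
- Hodges-Lehmann shift: (1 + 4)/2 = 2.5 h.
- Rank-sum 90% interval: 8th value 0 h, 29th value 9 h.

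Read literally, Table 102 would print 3.5 (0, 9). The estimate that belongs to that interval is 2.5.

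**Step 3: how often and by how much.** Lognormal Tmax was snapped to the nominal sampling times, with 10,000 datasets of 6 v 6 per row. The last two columns are population values before snapping.

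| Medians fasted / fed (h) | Log-SD fasted / fed | Estimates differ | Mean gap (h) | 95th percentile of gap (h) | Population difference in medians (h) | Population shift (h) |
|---|---|---|---|---|---|---|
| 4 / 4 | 0.4 / 0.4 | 58% | 0.41 | 1.0 | 0 | 0.00 |
| 4 / 6 | 0.4 / 0.4 | 60% | 0.48 | 1.5 | 2 | 1.93 |
| 4 / 8 | 0.4 / 0.7 | 64% | 0.54 | 1.5 | 4 | 3.85 |
| 4 / 6 | 0.3 / 0.8 | 60% | 0.44 | 1.0 | 2 | 1.95 |

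A wider set of assumptions (fasted median 4 to 6 h, fed 6 to 24 h, CV 30 to 80%) gave disagreement in 46 to 66% of datasets and mean gaps of 0.4 to 1.1 h. The larger gaps depend on the wider assumptions.

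**Step 4: can the printed estimate fall outside its interval?** Not at 6 v 6. Take the three largest fed values and the three smallest fasted values. Each of their 3 × 3 = 9 differences is at or above the difference in medians. By the mirror argument, nine are at or below it. The difference in medians therefore lies between the 9th and 28th ordered differences, inside the 8th-to-29th interval. This holds for any data, on nominal or actual times.

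**The case against.** The strongest reply is that this is a wording ambiguity with no consequence. Much of that stands.

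- The estimate cell in Table 102 is a blank in a mock-up, and SAP 10.3.2 does not say that the estimate is formed by subtracting sample medians. Subtraction is the natural reading of the estimand column, but it is an inference. It is also why the row needs to be explicit.
- Under a pure location shift the two population quantities coincide. The SAP does not state that model, and the sample estimates usually differ even when it holds: the first row of the table has identical distributions and still 58% disagreement.
- Fed v fasted PK is declared exploratory in protocol 10.2 and SAP 4.2 and 5. The no-food-effect criterion in SAP 10.3.3 covers Cmax and the two AUCs, not Tmax.
- SAP 10.2 uses actual sampling times, whereas the simulations use nominal ones, so the percentages are approximate. The mean gaps of about 0.4 to 0.5 h are also smaller than the 2 h spacing of samples from 4 to 14 h.
- The two group medians are not lost. Table 73 shows Tmax as median with range for 160 mg fasted and fed, and Table 80 repeats it for VT-11134.

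A reader might also infer that the two quantities separate whenever food changes the spread of Tmax. That is too strong: two symmetric distributions with unequal spread give the same answer, for example 4.00 for both with normal means 5 and 9 and unequal SDs. Skewness is needed as well, and nothing in the documents says how a meal would alter the shape of the Tmax distribution. Nor is the defect that the estimate is off-centre. In the example the Hodges-Lehmann value of 2.5 h is not the midpoint of 0 to 9 h (4.5 h) either, and 3.5 h is nearer to it. The point is correspondence, not centring.

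**Conclusion.** The mismatch is real and minor. Table 102 and SAP 10.3.2 label the quantity as a difference in medians and attach an interval whose corresponding estimate is the Hodges-Lehmann shift. Under the assumed distributions, the choice changes the reported number in roughly half to two thirds of 6 v 6 datasets, by about 0.4 to 0.6 h on average in most scenarios. The population values differ little (at most 4.00 v 3.85 h in the table above).

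A reader might go on to infer that the interval is invalid or could contradict the estimate. The evidence does not support that. At 6 v 6 the difference in medians cannot fall outside the interval, and in the wider simulations the interval covered the true difference in medians 92 to 99% of the time against a nominal 90%. A reader might also infer that a food-effect conclusion is at risk; no decision in either document rests on Tmax.

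The sizes rest on six evaluable subjects per group, lognormal Tmax and nominal sampling times. The mismatch itself rests only on the wording of the SAP.

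**What to change.** In the independent row of Table 102, for both analytes, report the Hodges-Lehmann estimate of the fed-minus-fasted shift with its exact rank-sum 90% CI. Relabel the estimand as the median of all fed-minus-fasted pairwise differences, and align the sentence in SAP 10.3.2. The group medians can stay where they are, in Tables 73 and 80, with a cross-reference if wanted.

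An acceptable alternative is to keep the difference in medians and specify an interval built for that quantity. That is more work for no evident gain.

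The preferred change costs one label and one statistic, computed from the same pairwise differences that give the interval. It needs no new data and no design change. As SAP 15 describes the test as already performed, it can be made in the study report table with a short note.
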